Prior to enrolling patients, each investigational center IRB will be required to approve the study Investigation Plan and the Patient Informed Consent. In addition, patients will be required to provide written informed consent for enrollment.

Patients will undergo a pre-implant baseline assessment to ensure they meet the inclusion and exclusion criteria prior to randomization. The baseline assessment must occur within 30 days prior to implant. Patient informed consent must be signed prior to conducting any screening or baseline testing procedure performed solely for study purposes. A screening number will be assigned upon consent. To minimize the burden to the patient, data collected as standard of care and not for the specific reason for assessing study eligibility may be used for baseline data points as outlined in the informed consent. These tests will suffice for the respective portion of the baseline dataset if collected within the pre-implant evaluation prior to randomization.

When a subject has met all Inclusion/Exclusion Criteria for the study, he/she will be randomized and assigned a randomization number by the center. The treatment subjects must proceed to implant within the window (≤ 30 days from consent to implant).

If the subject does not meet the inclusion/exclusion requirements, he/she will be study exited.

In accordance with the ethical principles that have their origin in the Declaration of Helsinki, each subject must be informed about the study and the patient or legal representative must sign and date an agreement acknowledging that participation in the study is voluntary. The Patient Informed Consent Form will be provided to the patient in the language he/she is able to read and understand. (Refer to Appendix E for the sample Consent Forms). The original signed Informed Consent will be retained in the individual Participant Study folders, and copies of the signed Informed Consent Form will be provided to the patient and to the hospital medical records of the patient.

Patients shall be consented for follow-up to five years.

Subject Withdrawal or Loss to Follow-Up

In the event a subject chooses to withdraw from the clinical study, the investigational site should attempt to ensure that any adverse events are resolved and documented as such. A Study Exit record must be completed and the subject will no longer be followed in the clinical study.

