In the event the subject becomes lost to follow-up, the investigational site should make two documented attempts to contact the subject. A Study Exit record must be completed and the subject will no longer be followed in the clinical study.

Data Collection Overview

A review of patient files is required to determine preliminary eligibility according to patient inclusion and exclusion criteria. Baseline data including functional tests must be collected no more than **30** days prior to randomization. Baseline imaging such as echo and CT scans must be collected no more than 90 days prior to randomization. See the data collection table for details.

Follow-up data will be collected at the time of implant, hospital discharge, at planned follow-ups (6 week, 3, 6, 12, 18-month and annually from the implant date thereafter up to 5 years). All serious adverse events will be collected throughout the study until closure.

All study subjects will follow the prescribed follow-up scheduled despite randomization. Day 0 for the treatment group will be the day of implant. Day 0 for the Control Group will be the day of randomization. Each group will continue with optimal medical therapy for the duration of the study, including all standard of care medications and treatments including transplant, VAD, etc. If the subjects are transplanted or placed on another device they will be censored from the primary endpoint analysis and study exited. Subjects implanted with the C-Pulse will be followed until device removal. If the PIL is explanted and not replaced, the subject will be followed for safety until removal of the entire system.

Data will be collected via electronic data capture (EDC) screens referred to as e-case report forms (eCRFs). Echocardiogram tapes and digital storage media must be documented in the patient medical record for source documentation.

Table 1, below outlines the data collection with the appropriate follow-up time windows.

Table 1. Follow-up Windows

Evaluation	Time Window
Pre-Implant Evaluation	No more than 30 days prior to implant
Randomization	Post Baseline Testing and Pre-Implant
Implant	Day 0 (Treatment Group) – Implant Day 0 (Control Group) – Randomization
Pre-Discharge	Within 36 hours prior to discharge
6 – week follow-up	Days 42 ± 7 Post-Implant
3 – month follow-up	Days 90 ± 14 Post-Implant
6 – month follow-up	Days 180 ± 30 Post-Implant
12 – month follow-up	Day 365 ± 30 Post-Implant
18 – month follow-up	Day 540 ± 30 Post-Implant

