Data collection regarding serious adverse events will be collected throughout the study. Upon identification, the investigator completes the adverse event information via the Adverse Event eCRF. Sunshine Heart Inc. clinical personnel or designee may request further information from the investigator if necessary for review of the event with the Clinical Event Committee (CEC).

The following information will be collected in the database: the date of event onset, the relationship of the event to the implant procedure, device, concomitant medications, patient management, or therapy, other actions taken as a result of the event, and the outcome of the event.

Adverse Event Definitions

Serious Adverse Event is defined as an adverse event that¹²;

- a) Led to death
- b) Lead to serious deterioration in the health of the subject, that either resulted in
 1. A life-threatening illness or injury, or
 2. A permanent impairment of a body structure or a body function, or
 3. In-patient or prolonged hospitalization, or
 4. Medical or surgical intervention to prevent life-threatening illness or injury or permanent impairment to a body structure or a body function

¹² ISO 14155:2011 section 3.37

- c) Led to foetal distress, foetal death or a congenital abnormality or birth defect

(Note: Planned hospitalization for a pre-existing condition, or a procedure required by the protocol, without serious deterioration in health, is not considered a serious adverse event)

Definitions are listed below for anticipated adverse events. The definitions are consistent with Version 2.2 adverse event definitions for the *INTERMACS*® registry with the exception of Major Bleeding which does not have a minimum standard of transfusion. Aortic Disruption has been added in addition to the *INTERMACS*® registry definitions as an additional screening for safety with respect to the C-Pulse unique application. Worsening Heart Failure has been added due to C-Pulse System not being a heart function replacement rather a heart assist device and based on the definition used by the CEC in the US Feasibility study.

Major Bleeding

An episode of suspected internal or external bleeding that results in one or more of the following:

1. death
2. re-operation
3. hospitalization
4. transfusion of red blood cells.

NOTE: Hemorrhagic stroke is considered a neurological event and not as a separate bleeding event.

Cardiac Arrhythmias

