Symptoms and signs of persistent right ventricular dysfunction [central venous pressure (CVP) > 18 mmHg with a cardiac index <2.0 L/min/m² in the absence of elevated left atrial/pulmonary capillary wedge pressure (greater than 18 mmHg), tamponade, ventricular arrhythmias or pneumothorax] requiring RVAD implantation; or requiring inhaled nitric oxide or inotropic therapy for a duration of more than 1 week at any time after implantation.

Worsening Heart Failure

A heart failure event that does not require hospitalization but requires visit to Emergency Department or Unscheduled Visit to Clinic including the following (not counted as a primary endpoint event):

- Signs and symptoms of worsening heart failure; and
- Treatment with intravenous heart failure therapy (including but not limited to diuretic or inotropic therapy)

A heart failure event requiring hospitalization including the following:

- Signs and symptoms of worsening heart failure; and
- Treatment with intravenous heart failure therapy (including but not limited to diuretic or inotropic therapy); and
- A minimum of one date change in the hospital or emergency room

Note: Signs and symptoms of worsening heart failure include but are not limited to shortness of breath, persistent cough or wheezing, edema, tiredness, and fatigue.

Arterial Non–CNS Thromboembolism

An acute systemic arterial perfusion deficit in any non-cerebrovascular organ system due to thromboembolism confirmed by one or more of the following:

- 1) standard clinical and laboratory testing
- 2) operative findings
- 3) autopsy findings

This definition excludes neurological events.

Venous Thromboembolism Event

Evidence of venous thromboembolic event (e.g. deep vein thrombosis, pulmonary embolism) by standard clinical and laboratory testing.

Wound Dehiscence

Disruption of the apposed surfaces of a surgical incision, excluding infectious etiology, and requiring surgical repair.

Other

An event that causes clinically relevant changes in the patient's health (e.g. cancer).

Adverse Event Classification

All reported serious adverse events will be classified by the investigator, based on the following categories:

- Relatedness (i.e. device, procedure, concomitant medication, patient management or therapy);
- Status (i.e. ongoing or resolved)

Device Related

An adverse event will be considered device related if it is a direct result of, or is affected by the presence (intended or otherwise) of the investigational device.

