where HR is the hazard ratio; the ratio of the C-Pulse treatment group worsening heart failure event hazard relative to the Control group worsening heart failure event hazard. This is designed to demonstrate that C-Pulse[®] therapy increases the freedom from worsening heart failure events as compared to Control as evidenced by a HR that is less than 1 and the upper bound of the two-sided 95% confidence interval for the HR excludes 1. All occurrences of worsening heart failure events will be included in the primary endpoint analysis. Details of the analysis methods can be found in the Statistical Analysis Plan.

Primary Efficacy Endpoint Sample Size

Sample size was estimated using SAS v9.2 software under two sided test for a difference in freedom from worsening heart failure. For the purposes of sample size estimation, a time to first event analysis was used to provide a conservative estimate of the required number of events and subjects. The minimum required sample size and total number of worsening heart failure events was calculated under the following assumptions:

- Significance level = 0.05
- Power = 0.80
- Proportion for 6 month freedom from worsening heart failure event in Control group = 0.72
- Underlying treatment effect on the hazard ratio scale: HR = 0.70
- Accrual time of 2.5 years
- Minimum follow-up of 12 months
- 10% Attrition per year
- 1:1 allocation ratio

Under the above assumptions a total of 265 subjects with at least one worsening heart failure events are required to be observed to ensure adequate power which indicates a total of 388 subjects randomized. As the primary analysis will include all worsening heart failure events in a multiple event analysis, the power for the detection of a difference in freedom from worsening heart failure event may be greater than 80%.

Justification for Primary Efficacy Endpoint Sample Size Assumptions

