The basis for the primary safety endpoint is from previous studies that had evaluated devices specific to surgical intervention and death.^{13,14} The IDE study for the HeartWare® Ventricular Assist System was designed to evaluate non-inferiority of the proportion of study patients alive on the originally implanted device, transplanted, or explanted for recovery at 180 days. This study did not evaluate the impact of surgical intervention and may not be an appropriate comparison. In the Heart Mate II study, survival rate and surgical intervention data was collected in patients throughout the study. Patients were followed to death or pump replacement or repair, whichever occurred first, regardless of whether they were transplanted or explanted. The Heart Mate II study does provide an appropriate safety measure comparison for the C-Pulse System as surgical intervention and death are accounted for. Table 4 outlines the percent survival rate and reoperation repair or device replacement observed in the Heart Mate II study.

Table 4. Heart Mate II Study Rates

Number of cumulative patient deaths*	Survival Rate
43	90/133 (67%)
Reoperation to Repair or Replace the Device	
45	88/133 (66.2%)

*Cumulative deaths included patients that were transplanted, explanted, or had their device exchanged.

Report Following 40 Randomizations and Follow-up to 6 Weeks

A report will be prepared to descriptively summarize early safety and efficacy data and will be prepared after the 20th implanted (treatment) subject has been followed to 6 weeks post-implant and at least 12 treatment subjects have completed the 6-month follow-up or have progressed to VAD, transplant or death by the time of the report. The report will be provided to the DSMB for review for the purpose of making a recommendation to Sunshine Heart Inc. with regards to continuation of study subject enrollment and follow-up. The report and the DSMB's recommendation will be provided to FDA for consideration. It is expected that subject enrollment and follow-up will continue while the DSMB and FDA review this report. This report will include, at a minimum:

- Summary of all adverse events reported within 6 weeks of randomization summarized by treatment group, seriousness, relatedness, type of event, severity and event resolution. All events will be adjudicated.
- Summary of all worsening heart failure events in the report cohort. All events will be adjudicated.

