The proportions of subjects within each randomization group with major cardiac events (myocardial infarction, heart failure and stroke) and the composite of major cardiac events or death will be computed. Ninety-five percent binomial exact confidence limits will be calculated and time to each of these endpoints will be described by Kaplan-Meier curves.

4. Adverse events

The frequency and rate (based on the Poisson distribution) of all adverse events will be summarized for each randomization group overall and by seriousness, severity, relatedness and expectedness. Differences in the incidence of adverse event rates will be compared between randomization groups using Poisson regression. Ninety five percent (95%) confidence intervals (based on the Poisson distribution) for the risk ratios will be computed. The number and proportion of subjects with adverse events well as the rate per patient year will be summarized.

5. Quality of life

Quality of life and changes from baseline as measured by the MLWHF and KCCQ assessments will be summarized by treatment group.

6. Device Performance and Usage

The device performance and subject usage will be summarized. The exchange of implanted components that did not result in a device malfunction adverse event will be reported. Device usage will be summarized as the percent of follow-up time with device use. This will be summarized as both a continuous outcome and in quartiles of use defined as 0-25%, 26-50%, 51-75% and 76-100%. The impact of device usage on the primary and secondary efficacy outcomes will be assessed within the C-Pulse arm by summarizing outcomes by quartile of use.

7. Reduction of diuretics

The dose of diuretics pre-implant and during support will be summarized for control and treatment groups.

8. ICD discharges

The frequency of ICD discharges will be summarized for control and treatment groups.

9. Summary of outcomes – Transplant, VAD Implantation, Recovery or Death

A competing outcomes summary will be completed demonstrating the occurrence of time to transplant, VAD implantation, Recovery or Death. Recovery will be defined as NYHA Class I/II and an Ejection Fraction greater than 40%. The data will be summarized for both the control and treatment groups.

Assessment of Poolability

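### The between-arm adverse event comparison includes worsening heart failure, the main efficacy event; add a randomized comparison without it

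*Combined protocol and SAP*

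**What the plan says.** Additional Supportive Analyses, item 4: "The frequency and rate (based on the Poisson distribution) of all adverse events will be summarized for each randomization group overall and by seriousness". The remaining splits are by expectedness, relatedness and severity. Rates are then compared between randomization groups by Poisson regression, with 95% intervals for the ratios. The item names no split by event type, no excluded event, no time window and no time origin.

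Adverse Event Definitions: "Worsening Heart Failure has been added due to C-Pulse System not being a heart function replacement rather a heart assist device". One branch of that definition begins "A heart failure event requiring hospitalization including the following". Heart failure hospitalization is a component of the primary efficacy endpoint, and an in-patient stay makes an event serious.

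Primary Safety Endpoint: implanted subjects only, compared with a performance goal of 0.60, so there is no control comparison.

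On timing, Data Collection Overview states that "Day 0 for the treatment group will be the day of implant", while control starts at randomization. Patient Informed Consent and Enrollment adds "The treatment subjects must proceed to implant within the window", which is at most 30 days from consent.

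The early report to the DSMB, planned after 40 randomizations, does split by type and counts from randomization: "Summary of all adverse events reported within 6 weeks of randomization summarized by treatment group, seriousness, relatedness, type of event, severity and event resolution".

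**The concern.** A between-arm adverse event ratio is normally read as a measure of harm. Here its numerator contains the event that the device is meant to prevent. A successful device lowers the ratio through its efficacy, whatever happens to bleeding, infection, renal dysfunction, arrhythmia and the other listed events. The serious-event ratio has the same feature, because heart failure admissions are serious.

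Surgery and a percutaneous lead are confined to one arm, so the natural safety question is whether non-heart-failure events are more frequent under randomization to the device, and by how much. The planned ratio answers that question and the efficacy question together. At stake is the clarity of a supportive safety analysis. Item 4 carries no alpha and has no stopping role.

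**Working it through.** **Inputs from Primary Efficacy Endpoint Sample Size.** "Proportion for 6 month freedom from worsening heart failure event in Control group = 0.72"; hazard ratio 0.70; accrual 2.5 years; minimum follow-up 12 months; "10% Attrition per year"; 194 subjects per arm.

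**The plan's own figure.** The control hazard is h = −2 ln(0.72) = 0.657 per year, and the device-arm hazard is 0.70 × 0.657 = 0.460. The Schoenfeld formula gives 247 events for 80% power. The average event probability with attrition is 0.624 to 0.627, so N = 247/0.627 = 394 to 247/0.624 = 396, against the stated 388. Power at 388 is 0.79. The inputs therefore reproduce the design closely. (The stated 265 events match the expected count without attrition, 388 × 0.685 = 265.8. This does not affect the present point.)

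**Assumptions.** The documents give no background rate b of non-heart-failure events, so I take 0.5, 1.0 and 2.0 per year. The composite first-event hazard h stands in for the heart failure event rate.

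**Break-even.** At the design effect the device removes 0.3 × 0.657 = 0.197 heart failure events per patient-year. Let R be the non-heart-failure rate ratio. The all-event ratio is (R·b + 0.7h)/(b + h). Setting it to 1 gives R = 1 + 0.3h/b.

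| b per year | Heart failure share of control events, h/(h+b) | R when all-event ratio = 1.00 | Same, with h halved |
|---|---|---|---|
| 0.5 | 57% | 1.39 | 1.20 |
| 1.0 | 40% | 1.20 | 1.10 |
| 2.0 | 25% | 1.10 | 1.05 |

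These values do not depend on follow-up length.

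**What the two comparisons would show.** Take b = 1.0 and a true R of 1.3. The all-event ratio is (1.3 + 0.460)/(1.0 + 0.657) = 1.06, with about 12% power. The ratio without heart failure is 1.30, with about 78% power. This uses a Wald test on the log rate ratio, 194 patient-years per arm and no overdispersion.

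**Effect of the window.** Suppose the extra device-arm events are a fixed number x per subject, assumed to be 0.40. With attrition only (0.105 per year), mean follow-up is f = 0.949 years within the first 12 months and 1.98 years over planned follow-up, assuming uniform accrual. The all-event ratio is [x + (0.7h + b)f]/[(h + b)f], and the ratio without heart failure is (x + bf)/(bf).

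- b = 0.5: 1.19 against 1.84 at 12 months; 1.00 against 1.40 over full follow-up.
- b = 2.0: 1.08 against 1.21 at 12 months; 1.00 against 1.10 over full follow-up.

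The value x = 0.40 lies close to the heart failure events avoided over full follow-up (0.197 × 1.98 = 0.39 per subject), so the 1.00 follows from the input. What the illustration shows is that the all-event ratio depends on when the data are cut.

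**The case against.** The strongest reply is that the plan already shows the harm in other places. Item 4 has relatedness rows, and events attributed to device, procedure or therapy appear there undiluted by heart failure. Item 1 reports the heart failure hospitalization rate per patient-year. Mortality, MI and stroke are summarized by arm. The two days-alive endpoints differ by non-heart-failure hospital days. Exit-site infection has an early halt rule. Subtracting the heart failure hospitalization rate from the serious-event rate gives an approximate non-heart-failure serious rate in each arm. All of this stands, and a reader who infers that the plan conceals harm goes further than the documents allow. Subtraction does not give a ratio with a confidence interval. Device, procedure and therapy rows rest on attribution and are near zero in control, so they do not compare events that both arms can have.

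A reader might also infer that every relatedness row is empty in control. It is not: patient-management and concomitant-medication relatedness apply to both arms.

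A third tempting inference is that the arm-specific Day 0 drops treatment-arm events before implant. Nothing in the documents starts adverse event time at Day 0. Serious events are collected throughout, item 4 is by randomization group, and the early report and the days-alive endpoints run from randomization. The origin for item 4 is unstated, not wrong.

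Finally, item 4 does not say which strata enter the regression. The protocol refers details of other analyses to a Statistical Analysis Plan, and no separate text of it is in the documents reviewed. It may add what is asked for here, although item 4 does not cite it.

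**Conclusion.** The point holds as a cheap improvement to supportive safety reporting. It does not threaten the primary efficacy or primary safety result.

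At the design heart failure effect, an all-event ratio of 1.00 is compatible with a non-heart-failure ratio of about 1.1 to 1.4 for background rates of 2.0 down to 0.5 per year, or 1.05 to 1.20 if the heart failure rate is half the proxy. Those background rates are assumed. The proxy is a composite first-event hazard that also covers death, LVAD and transplant, so it is not a heart failure hospitalization rate. Recurrent heart failure events and heart failure visits without admission would push the offset up. The offset arises only if the device reduces heart failure events, and it is small when background rates are high. In the illustration it also leaves an all-event excess visible at a 12-month cut.

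What the stated plan lacks is narrow: a direct randomized estimate, with a confidence interval, of events other than heart failure.

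**What to change.** Keep item 4 as written and add:

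- A between-arm Poisson comparison of (serious) adverse events excluding worsening heart failure, with a follow-up-time offset, through 12 months and over all follow-up. Show the all-event ratio beside it, because the new result depends on whether an event is adjudicated as heart failure.
- A sentence stating that time is counted from randomization in both arms. This clarifies an unstated origin.
- A descriptive table of each defined event type by arm, including worsening heart failure. Note that several definitions (for example hemolysis, hepatic dysfunction, perioperative MI, respiratory failure) and the Table 3 exemptions are anchored to implant, so those rows are not like-for-like in control.

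The cost is analysis-plan wording and a few tables; onset dates and committee adjudication are already planned. Counts will be small for some types. Since the protocol mostly describes collecting serious events, separate all-event and serious-event versions may largely coincide, and one may suffice.
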